6.3.1 Leukemia mutation panel

As a standard of care all AML patients at MDACC are evaluated for karyotype and molecular mutation profile using a CLIA-certified next-generation gene sequencing platform. The effects of the combination will be compared not only to historical outcomes in matched groups of patients,

but also at the molecular and cellular level by correlating with karyotype and molecular mutation profile. The Leukemia mutation panel will be performed on the screening BM aspirate and the progression/relapse BM aspirate. An aliquot of DNA will be stored for additional analysis of DNA mutations in responding patients, if these are not identified by the Leukemia mutation panel.

6.3.2 Minimal Residual Disease assessment by flow-cytometry

As a standard of care all BM aspirates will be evaluated for MRD by validated 17-color multiparameter multicolor flow-cytometry.

6.3.3 Gene expression perturbations by RNA sequencing and targeted QPCR analyses

ATAC-Seq, RNA-Seq and targeted QPCR analyses will be performed on the pre-treatment and on study bone marrow and peripheral blood at study defined timepoints to evaluate the hypothesis that concurrent therapy with venetoclax and OM will be synergistically lethal against AML stem progenitor cells.

RNA-Seq analyses will be conducted utilizing Illumina HiSeq4000 platform in the Sequencing and Microarray Facility of MDACC. Additionally, gene set enrichment analyses (GSEA) will be conducted to determine specific pathways affected by the treatments. We will infer specific enriched pathways using the Gene-Set Enrichment (GSEA) method and the gene-set collection from the Molecular Signature Database (MSigDB). (Liberzon et al., 2015; Subramanian et al., 2005) The transcriptional perturbations will be confirmed by QPCR analyses.

6.3.4. Protein Expression Analyses by RPPA, CyTOF, Flow cytometry and Confocal Microscopy.

RPPA will be performed utilizing curated and highly validated antibodies against approximately 300 proteins in the Functional Proteomics RPPA core facility at the MD Anderson Cancer Center, as previously reported.(Saenz et al., 2017) Mass cytometry 'CyTOF' analysis of pre- and post-treatment, paraformaldehyde-fixed and permeabilized cells, stained with a cocktail of antibodies conjugated to transition element isotopes used as tags, will be conducted at the Flow Cytometry and Cellular Imaging (FCCI) Core Facility at MDACC. Time-of-flight mass spectrometry measures the different cellular parameters, simultaneously in each cell, and the changes in the normalized mass cytometry data between untreated and treated cells are organized in an unsupervised manner using SPADE (spanning-tree progression analysis of density-normalized events) and displayed as heatmaps relative to the untreated control cells as previously reported.(Behbehani et al., 2015; Saenz et al., 2017) Pre- and post-treatment (Day 0, Day 2 and Day 5) AML cells will also be fixed with paraformaldehyde and permeabilized with

Protocol 2020-0890

Version 3

Dated 08/07/2024

methanol for subsequent Flow Cytometric analyses, to determine the surface and intracellular expressions of proteins.

Additional material will be stored in [name] laboratory for potential studies of interest.

7.0 REGULATORY AND REPORTING REQUIREMENTS

7.1 Informed Consent:

Before a subject's participation in the clinical study, the investigator is responsible for obtaining written informed consent from the subject or legally acceptable representative after adequate explanation of the aims, methods, anticipated benefits, and potential hazards of the study and before any protocol-specific screening procedures or any investigational products are administered. A legally acceptable representative is an individual or other body authorized under applicable law to consent, on behalf of a prospective subject, to the subject's participation in the clinical study.

The acquisition of informed consent should be documented in the subject's medical records, and the informed consent form should be signed and personally dated by the subject or a legally acceptable representative and by the person who conducted the informed consent discussion. The original signed informed consent form should be retained in accordance with institutional policy, and a copy of the signed consent form should be provided to the subject or legally acceptable representative. All consented participants will be registered in the Clinical Oncology Research System (CORe)

7.2 Independent Ethics Committee/Institutional Review Board

A copy of the protocol, proposed informed consent form, other written subject information, and any proposed advertising material must be submitted to the IEC/IRB for written approval.

The investigator must submit and, where necessary, obtain approval from the IEC/IRB for all subsequent protocol amendments and changes to the informed consent form. The investigator should notify the IEC/IRB of deviations from the protocol or serious adverse events occurring at the site.

The investigator will be responsible for obtaining annual IEC/IRB approval/renewal throughout the duration of the study.

7.3 Subject Confidentiality

In compliance with ICH GCP Guidelines, it is required that the investigator and institution permit authorized representatives of the regulatory agency(s), and the IEC/IRB direct access to review the subject's original medical records for verification of study-related procedures and data. Direct access includes examining, analyzing, verifying, and reproducing any records and reports that are important to the evaluation of the study. The investigator is obligated to inform and

obtain the consent of the subject to permit named representatives to have access to his/her study-related records without violating the confidentiality of the subject.

7.4 Study Documentation and Archival

The investigator should maintain a list of appropriately qualified persons to whom he/she has delegated study duties. All persons authorized to make entries and/or corrections on case report forms will be included on the Delegation of Authority Form.

Source documents are original documents, data, and records from which the subject's case report form data are obtained. These include but are not limited to hospital records, clinical and office charts, laboratory and pharmacy records, diaries, microfiches, radiographs, and correspondence. Case report form entries may be considered source data if the CRF is the site of the original recording (ie, there is no other written or electronic record of data).

The investigator and study staff are responsible for maintaining a comprehensive and centralized filing system of all study-related (essential) documentation, suitable for inspection at any time by applicable regulatory authorities. Elements should include:

- Subject files containing completed case report forms, and subject identification list
- Study files containing the protocol with all amendments, investigator's brochure, copies of pre-study documentation and all correspondence to and from the IEC/IRB

7.5. Adverse Events:

7.5.1 Monitoring, recording and reporting adverse events

An adverse event (AE) is any noxious, unintended, or untoward medical occurrence that may appear or worsen in a subject during the course of a study. It may be a new intercurrent illness, a worsening concomitant illness, an injury, or any concomitant impairment of the subject's health, including laboratory test values, regardless of etiology. A diagnosis or syndrome should be recorded rather than the individual signs or symptoms of the diagnosis or syndrome.

All subjects will be monitored for AEs during the study. Assessments may include monitoring of any or all of the following parameters: the subject's clinical symptoms, laboratory, pathological, radiological or surgical findings, physical examination findings, or findings from other tests and/or procedures. The Investigator or physician designee is responsible for verifying and providing source documentation for all adverse events and assigning the attribution for each event for all subjects enrolled on the trial.

AEs will be recorded by the Investigator from the time the subject signs informed consent until 30 days after the last dose of IP and those SAEs made known to the investigator at any time

thereafter that are suspected of being related to IP. AEs and serious adverse events (SAEs) will be recorded in the subject's source documents. The Leukemia-specific Adverse Event Recording and Reporting Guidelines will be followed for the recording and reporting of adverse and serious adverse events.

1. Baseline events will be recorded in the medical history section of the case report form (Prometheus) and will include the terminology event name, grade, and start date of the event. The medical history section of the case report form will serve as the source document for baseline events once signed and dated by the principal investigator.
 - a. Baseline events are any medical condition, symptom, or clinically significant lab abnormality present before the informed consent is signed
 - i. Hematologic laboratory abnormalities will not be recorded as baseline events for patients with acute leukemia, myelodysplastic syndrome, chronic lymphocytic leukemia, or chronic myeloid leukemia in blast phase.
 - ii. If exact start date is unknown, month and year or year may be used as the start date of the baseline event.
2. The maximum grade of the adverse event will be captured per course or protocol defined visit date.
3. These adverse events will be recorded in the case report form:
 - a. Any grade adverse event that is possibly, probably, or definitely related to the study drug(s).
 - b. All serious adverse events regardless of attribution to the study drug(s).
 - c. Any grade adverse event regardless of attribution to the study drug(s) that results in any dose modification.
4. Hematologic adverse events will not be recorded or reported for studies in patients with acute leukemia, myelodysplastic syndrome, chronic lymphocytic leukemia, or chronic myeloid leukemia in blast phase except for:
 - a. Prolonged myelosuppression as defined by the NCI-CTCAE criteria specific for leukemia, e.g. marrow hypocellularity on day 42 or later (6 weeks) from start of therapy without evidence of leukemia (< 5% blasts), or that results in dose modifications, interruptions or meets the protocol definition of SAE.
5. Serious adverse events will be reported according to institutional policy.
6. Protocol specific language regarding the recording and reporting of adverse and serious adverse events will be followed in the event of discordance between the protocol and Leukemia-specific adverse event recording and reporting guidelines.

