This study will be a Phase 1b/II single center, open-label, non-randomized clinical trial with the dual primary objectives of assessing the safety and efficacy of omacetaxine in combination with the BCL2 inhibitor venetoclax for patients with RUNX1-mutated relapsed or refractory AML or MDS. Up to 12 cycles will be administered.

Patients will be instructed to self-administer OM at home and return unused intact drug syringes to be disposed of by the study staff. Patients will be given a Research Medication Diary to record the medication taken each day. Patients will be instructed to bring the diary and any unused intact medication syringes with them to all study visits. Any unused drug will be disposed of per institutional standard practice.

4.2 Phase 1b Portion:

A maximum of 12 patients will be treated in Arm A (AML) and Arm B (MDS), respectively. Patients will be enrolled in cohorts of 3 within each arm. The starting dose in both arms will evaluate omacetaxine via subcutaneous injection at a dose of 1.25 mg/m² twice daily for 3 consecutive days on days 2-4, in combination with venetoclax 400mg orally daily on days 1-10 per treatment cycle.

The RP2D will be selected at the end of the Phase 1b portion based on safety data, in Arms A and B independently. Preliminary efficacy and PK data for each dose level may also be considered as appropriate. Once the RP2D has been identified, that Arm will transition to the respective Phase 2 portion.

Table 1 below shows the planned dose levels, with the starting dose being dose level 0. Patients treated in the Phase 1b portion that are removed from study before day 28 for any reason other than toxicity, and have not experienced DLT, will be replaced.

Table 1: Dose de-escalation for omacetaxine and venetoclax

Dose Level	omacetaxine	venetoclax
+1	1.25 mg/m ² BID days 2-4	400mg QDAY days 1-14
0 (starting dose)	1.25 mg/m ² BID days 2-4	400mg QDAY days 1-10
-1	1.25 mg/m ² BID days 2-3	400mg QDAY days 1-10
-2	1.25 mg/m ² BID days 2-3	400mg QDAY days 1-7

Dose levels outside of this table may be considered based on review of patient safety and efficacy and PK data and will be detailed in a subsequent amendment, if applicable.

4.3 Phase 2:

Up to 60 patients will be treated; up to 30 patients with AML (Arm A) and up to 30 patients with MDS (Arm B) at the recommended Phase 2 dose level. Note that based on the Phase 1b portion, the dose level for the Phase 2 portion of Arm A and Arm B may not be the same.

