6.2.1. Definition of Dose-Limiting Toxicity

A dose-limiting toxicity (DLT) is defined as any grade 3 or higher non-hematologic adverse event or abnormal laboratory value occurring during the first cycle on study that cannot be attributed by the investigator to a clearly identifiable cause such as disease progression, underlying illness, concurrent illness, or concomitant medication, with the following exceptions:

- Grade 3 nausea, vomiting or diarrhea that can be managed to < Grade 3 within 7 days with standard antiemetic or antidiarrheal medications
- Grade 3 or 4 electrolyte abnormalities will only be considered DLT if possibly related to study drug, extend beyond 72 hours, and are not corrected by optimal replacement therapy. Venetoclax interruption for up to 72 hours following transient (< 48 hours) chemical changes and laboratory TLS may be allowed and may not be considered a DLT.

Confirmed Hy's law cases will be considered as DLT. A positive Hy's law case is defined as AST or ALT $\geq 3 \times$ ULN in the setting of total bilirubin $\geq 2 \times$ ULN, without findings of cholestasis, and no other reason can be found to explain the combination of increased aminotransferases and total bilirubin, such as viral hepatitis A, B, or C, preexisting or acute liver disease, or another drug capable of causing the observed injury.

Hematologic DLT is defined as Grade ≥ 4 neutropenia and/or thrombocytopenia and no greater than 5% marrow blasts lasting for 6 weeks or more after the start of a course in the absence of underlying MDS. Anemia will not be considered for the definition of DLT.

Patients with neutropenia or thrombocytopenia as a consequence of the disease prior to the start of therapy do not require treatment interruptions for myelosuppression. Dose reductions of the study treatment in these patients may be considered on an individual case basis and discussed with the PI.

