6.2.2 Serious Adverse Event (SAE) Reporting Requirements for M D Anderson Sponsored protocol

An adverse event or suspected adverse reaction is considered "serious" if, in the view of either the investigator or the sponsor, it results in any of the following outcomes:

- Death
- A life-threatening adverse event
- Inpatient hospitalization or prolongation of existing hospitalization
- A persistent or significant incapacity or substantial disruption of the ability to conduct normal life functions.
- A congenital anomaly/birth defect.

Important medical events that may not result in death, be life-threatening, or require hospitalization may be considered a serious adverse drug experience when, based upon appropriate medical judgment, they may jeopardize the patient or subject and may require medical or surgical intervention to prevent one of the outcomes listed in this definition.

Examples of such medical events include allergic bronchospasm requiring intensive treatment in an emergency room or at home, blood dyscrasias or convulsions that do not result in inpatient hospitalization, or the development of drug dependency or drug abuse (21 CFR 312.32).

- Important medical events as defined above, may also be considered serious adverse events. Any important medical event can and should be reported as an SAE if deemed appropriate by the Principal Investigator or the IND Sponsor, IND Office.
- All events occurring during the conduct of a protocol and meeting the definition of a SAE must be reported to the IRB in accordance with the timeframes and procedures outlined in "The University of Texas M. D. Anderson Cancer Center Institutional Review Board Policy on Reporting Adverse Events for Drugs and Devices".

- Serious adverse events will be captured from the time of the first protocol-specific intervention, until 30 days after the last dose of drug or protocol specific timeline, unless the participant withdraws consent.
- Serious adverse events must be followed until clinical recovery is complete and laboratory tests have returned to baseline, progression of the event has stabilized, or there has been acceptable resolution of the event.
- All SAEs, expected or unexpected/ initial or follow up, must be reported to the IND Office **within 5 working days of knowledge of the event** regardless of the attribution.

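### In a patient's final course, at every planned dose level except +1, routine adverse event recording closes 2 to 5 days before prolonged myelosuppression can meet its day-42 criterion

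*Combined protocol and SAP*

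**What the plan says.** Section 7.5.1 gives one AE window per patient: "AEs will be recorded by the Investigator from the time the subject signs informed consent until 30 days after the last dose of IP". After that it keeps only drug-related serious events: "and those SAEs made known to the investigator at any time" later. Section 6.2.2 uses the same limit for SAEs, "until 30 days after the last dose of drug or protocol specific timeline", and also asks for later related SAEs to be reported.

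Item 4 of section 7.5.1 excludes hematologic events from recording in these diseases, with an exception for prolonged myelosuppression. The example given is "marrow hypocellularity on day 42 or later (6 weeks) from start of therapy without evidence of leukemia" (fewer than 5% blasts). The exception extends to myelosuppression "or that results in dose modifications, interruptions or meets the protocol definition of SAE".

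Section 6.2.1 defines hematologic DLT as grade 4 or worse neutropenia or thrombocytopenia, with marrow blasts no higher than 5%, "lasting for 6 weeks or more after the start of a course", and only where there is no underlying MDS.

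Dosing is confined to the start of each course. Section 4.2 starts both arms with omacetaxine on days 2-4 "in combination with venetoclax 400mg orally daily on days 1-10 per treatment cycle". The longest schedule in Table 1, level +1, gives venetoclax "400mg QDAY days 1-14".

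**The concern.** The window is counted from the last dose, whereas the criterion is counted from the start of therapy or of the course. With dosing over by day 7 or 10, the two clocks do not meet. Item 4 keeps an uncomplicated cytopenia out of the record until it qualifies as prolonged, and by then routine recording has closed. Follow-up after stopping does not fill the gap. Section 4.4.3 continues survival follow-up only, section 7.5.1.4 follows unresolved SAEs only, and the Table of Events schedules no blood count after the end-of-study visit.

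Prolonged myelosuppression is the one hematologic toxicity that the plan singles out for recording, and the only one that can be a DLT. A gap here can only lower its reported frequency. The patients concerned are foreseeable: section 4.4.1 lists possible transplant, intercurrent illness and patient decision among the reasons to stop.

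**Working it through.** **Inputs**
- End of routine recording: last dose of study drug + 30 days (sections 7.5.1 and 6.2.2).
- Last dosing day by level (Table 1, section 4.2): venetoclax day 14 (+1), day 10 (0 and -1), day 7 (-2). Omacetaxine ends on day 4 (+1 and 0) or day 3 (-1 and -2), so venetoclax sets the last dose at every level.
- Individual venetoclax reductions: 10, 7 or 5 days (Table 2, section 5.7).
- One agent may be stopped and the other continued (section 4.4.2). Omacetaxine alone then ends on day 4 or day 3.
- Cycle length: 4-6 weeks (section 4.3).

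**The plan's own figure.** 6 weeks × 7 = 42 days, which agrees with item 4a.

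**Window end in a patient's final course** = last dosing day + 30. Shortfall = 42 − window end.

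| Schedule in the final course | Last dose | Window ends | Shortfall |
|---|---|---|---|
| Level +1 | day 14 | day 44 | none (2 days to spare) |
| Level 0 | day 10 | day 40 | 2 days |
| Level -1 | day 10 | day 40 | 2 days |
| Level -2 | day 7 | day 37 | 5 days |
| 5-day venetoclax reduction | day 5 | day 35 | 7 days |
| Omacetaxine alone, through day 4 | day 4 | day 34 | 8 days |
| Omacetaxine alone, through day 3 | day 3 | day 33 | 9 days |

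The last dose must fall on day 42 − 30 = 12 or later for the window to reach day 42. Of the Table 1 levels, only +1 does so.

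**Patients who are dosed again.** Counted from cycle 1 day 1, with n cycles of length L, the window ends on day (n − 1) × L + last dosing day + 30. For two 28-day cycles this gives 28 + 7 + 30 = day 65 at level -2 and 28 + 10 + 30 = day 68 at level 0. Day 42 of cycle 1 is therefore covered for anyone who starts cycle 2.

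**What one uncounted event could do, if DLTs are drawn from the AE record.** In the phase 1b escalation table (Table 4, section 8.0), 1 DLT in 3 patients means stay and 0 in 3 means escalate. In the AML phase 2 boundaries (also numbered Table 4), 2 toxicities in 6 patients means stop and 1 in 6 means continue. Section 4.2 replaces patients removed before day 28 for reasons other than toxicity, so one who stops between day 28 and day 42 is not replaced under that rule.

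**The case against.** The strongest reply is that most of the patients one would worry about are already covered.

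- The window is per patient, not per course, so re-dosed patients are covered. This stands.
- Day 42 is an example in item 4a. Myelosuppression that leads to an interruption or dose modification, or is serious, has no day condition. This stands, and it narrows the gap considerably.
- Section 5.2.4 calls for a marrow at day 28 (± 7 days). If leukemia has cleared, venetoclax is held, and the marrow is repeated about two weeks later when counts have not recovered. The hold is arguably a recordable interruption, and the repeat falls near day 42. This helps patients who are still under evaluation for further treatment. It does not clearly reach a patient who has stopped permanently.
- Section 7.5.1.5 makes the investigator follow events until resolution, section 7.5.1.2 asks for stop dates, and the cytopenia begins inside the window. This does not close the gap, because item 4 keeps the cytopenia out of the record until it qualifies.
- At levels 0 and -1 the shortfall is two days, less than the visit windows for blood counts (± 4 days) and marrow (± 7 days). True, but those windows govern when a test is done, not whether its result is recorded.

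A reader might also infer that DLT counts are biased in both arms. The documents do not support that. No section says that the AE window cuts short the DLT assessment in section 6.2.1. That definition also requires the absence of underlying MDS, so the 6-patient example should not be carried over to the MDS boundaries in Table 6.

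**Conclusion.** The gap is real but narrow. In a patient's final course, routine recording ends 2 days before day 42 at levels 0 and -1 and 5 days before it at level -2. The shortfall is larger under the 5-day venetoclax reduction or with omacetaxine alone. What falls through is non-serious prolonged myelosuppression without leukemia in a patient who stops for good with no recorded interruption or dose change. Recording can be incomplete in both arms, and only downward. A lower hematologic DLT count is a possible consequence, mainly in the AML arm, and only if DLTs are taken from the AE record.

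A reader might infer that every patient whose last course is not followed by another is affected. That goes too far: item 4a requires fewer than 5% blasts, so patients who stop with persistent or progressive leukemia cannot have the day-42 event. The number affected cannot be derived from the documents.

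Two readings matter. I take day 42 as equal to six weeks, as item 4a does. If start of therapy in item 4a means cycle 1 day 1, its gap is limited to patients who receive one cycle. The start-of-course wording in section 6.2.1 would still expose any last course within cycles 1-3, the period over which phase 2 monitors DLTs.

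**What to change.** Reconcile sections 6.2.1, 6.2.2 and 7.5.1:

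1. End AE and SAE collection at the later of 30 days after the last dose and day 42 of the last course.
2. State that hematologic DLT assessment runs to day 42 of the course regardless of the AE window.
3. Say whether start of therapy in item 4a means cycle 1 day 1 or the start of the current course.
4. For the assessment, use the weekly blood counts of the first two cycles (Table of Events, footnote b) and the repeat marrow in section 5.2.4, both of which already fall around that time. State that results obtained up to day 42 are recorded after treatment has stopped.

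The cost is wording in three sections and a few more days of collection: 2 to 5 at the Table 1 levels concerned, up to 9 with omacetaxine alone. Some late cytopenias will need attribution to drug or disease.

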Platelet response (pretreatment, $< 100 \times 10^9/\text{L}$)	Absolute increase of $\geq 30 \times 10^9/\text{L}$ for patients starting with $> 20 \times 10^9/\text{L}$ platelets Increase from $< 20 \times 10^9/\text{L}$ to $> 20 \times 10^9/\text{L}$ and by at least 100%†
Neutrophil response (pretreatment, $< 1.0 \times 10^9/\text{L}$)	At least 100% increase and an absolute increase $> 0.5 \times 10^9/\text{L}$ †
Progression or relapse after HI‡	At least 1 of the following: At least 50% decrement from maximum response levels in granulocytes or platelets Reduction in Hgb by $> 1.5 \text{ g/dL}$ Transfusion dependence

Source: ([Cheson, et al. 2006](#)) Abbreviations: Hgb indicates hemoglobin; RBC: red blood cell; HI: hematologic improvement. Pretreatment counts averages of at least 2 measurements (not influenced by transfusions) ≥ 1 week apart (modification).

†Modification to IWG response criteria ([Cheson, et al. 2003](#)) ‡In the absence of another explanation, such as acute infection, repeated courses of chemotherapy (modification), gastrointestinal bleeding, hemolysis, and so forth.

6.2 Primary Safety Analysis:

The overall incidence and severity of all adverse events using Common Toxicity Criteria v 5.0

An adverse event is any untoward medical occurrence that may present during treatment with a pharmaceutical product but which does not necessarily have a causal relationship with this treatment.

Adverse drug reaction is a response to a drug which is noxious and unintended and which occurs at doses normally used in man for prophylaxis, diagnosis, or therapy of disease or for the modification of physiologic function.

Assessing causal connections between agents and disease is fundamental to the understanding of adverse drug reactions. In general, a drug may be considered a contributory cause of an adverse event if, had the drug not been administered, 1) the event would not have happened at all, 2) the event would have occurred later than it actually did, or 3) the event would have been less severe.

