8.4.2. Efficacy Evaluable Population

All patients who complete at least one post-baseline disease status assessment or who discontinue study medication early due to study drug-related toxicity will be considered evaluable for efficacy. Patients who do not meet the aforementioned requirements will be considered non-evaluable for response and may be replaced.

In addition, we will perform a sensitivity analysis for the efficacy endpoint which will include all patients who have received at least one dose of the study treatment (i.e., those who drop off study early due to any reason will be counted as non-responders).

8.4.3. DLT-evaluable population:

Unless doses are missed in Cycle 1 due to DLT(s), a patient must receive at least 70% of the planned doses of venetoclax and omacetaxine to be considered evaluable for DLT. If a patient received fewer doses/days of treatment in the first cycle of treatment for reasons other than a DLT, the patient will be considered non-evaluable for DLT and replaced.

8.5 Analysis Plan:

Descriptive statistics including plots, mean, median and standard deviations will be used to summarize data. For the primary efficacy analysis, we will estimate the ORR for the combination treatment, along with the Bayesian 95% credible interval. The priors for ORR will be (0.2, 0.8) for AML cohort and (0.15, 0.85) for MDS cohort. Event-free survival (EFS) is defined as the time interval between the date of treatment start and the date of [treatment failure, relapse or death from any cause](#). The Kaplan-Meier method will be used to estimate the probabilities of event-free survival (EFS) and overall survival (OS). Log-rank tests will be used to compare among subgroups of patients in terms of EFS or OS. Similar analyses will be performed for the duration of response. MRD negative status and exploratory biomarkers will be summarized graphically and with descriptive statistics. The association between molecular and cellular markers and overall response and/or resistance will be assessed through logistic regression analyses. Paired t-test or Wilcoxon signed rank test will be used to assess the marker change over time. Safety data will be summarized using frequency and percentage, by category and severity.

The Investigator is responsible for completing an efficacy/safety summary report, and submitting it to the IND Office Medical Affairs and Safety Group, for review and approval

- Phase 1b

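### Section 6.2 promises the incidence of all adverse events, but the CRF rules in 7.5.1 collect a narrower set and can leave out a rare type of DLT

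*Combined protocol and SAP*

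**What the plan says.** - **Endpoint.** Section 6.2 (Primary Safety Analysis) gives "The overall incidence and severity of all adverse events using Common Toxicity Criteria v 5.0" and defines an adverse event without requiring a causal link to treatment. Section 8.5 adds only that "Safety data will be summarized using frequency and percentage, by category and severity".
- **CRF classes.** Section 7.5.1 item 3 is a list of three classes to be entered in the CRF. Class (a) reads "Any grade adverse event that is possibly, probably, or definitely related to the study drug(s". Class (b) takes serious events whatever their attribution, and class (c) takes events, again whatever their attribution, that led to a change of dose.
- **Hematologic exclusion.** Item 4 states: "Hematologic adverse events will not be recorded or reported for studies in patients with acute leukemia, myelodysplastic syndrome". The exception covers prolonged myelosuppression and events that lead to dose modification, interruption or a serious event.
- **Source documents.** The opening of 7.5.1 has adverse events recorded in the subject's source documents.
- **DLT test.** Under 6.2.1, a first-cycle non-hematologic event or laboratory value of grade 3 or higher is a DLT if it is one "that cannot be attributed by the investigator to a clearly identifiable cause", with listed exceptions.
- **Attribution scale.** Section 7.5.1.5 has five levels. The two lowest, *unlikely* and *unrelated*, fall outside class (a).

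**The concern.** The endpoint and the data collection rule describe different sets of events. In a single-arm study attribution is a judgement with no control group to check it against. A table that keeps non-serious events only if they were judged related or changed a dose, but is titled as all events, will read as a lower event rate than patients experienced.

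The DLT definition and class (a) also use different attribution tests. One asks whether some other cause is evident. The other asks whether the study drug is at least possibly responsible. An event can pass the first and fail the second. DLT counts drive dose assignment in phase 1b and toxicity monitoring in phase 2, where decisions turn on one or two patients.

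**Working it through.** **Step 1. Which events does the CRF leave out?**

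- Non-serious, rated *unlikely* or *unrelated*, no dose change: fails (a), (b) and (c).
- Hematologic events outside the item 4 exception: excluded even if related to study drug.

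Both groups belong to the 6.2 endpoint. Item 6 of 7.5.1 does not settle the conflict. It ranks the protocol above the departmental reporting guideline, whereas 6.2 and 7.5.1 are both protocol text.

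**Step 2. Can a DLT fall outside the CRF list?** Take a non-serious, grade 3, non-hematologic event in cycle 1, outside the 6.2.1 exceptions, rated *unlikely*, with no evident alternative cause and no dose change.

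- Section 6.2.1: it is a DLT.
- Class (a): no, because *unlikely* is below *possible*.
- Class (b): no, because it is not serious.
- Class (c): no. The dose-adjustment rules in 4.4.2 address drug-related toxicity, so nothing forces a dose change here.

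Section 7.5.1.5 treats a doubtful drug relationship and a sufficient alternative explanation as separate grounds, so this combination is one the protocol recognises. No DLT-specific form is described. Hematologic DLTs are mostly covered by the item 4 exception, although the blast limits differ slightly (up to and including 5% in 6.2.1, below 5% in item 4).

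**Step 3. What does one missed DLT do in BOIN?** Inputs from Section 8.0: φ = 0.30, φ1 = 0.18, φ2 = 0.42.

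- Escalation boundary: log[(1−φ1)/(1−φ)] / log[φ(1−φ1)/(φ1(1−φ))] = log(0.82/0.70) / log(0.246/0.126) = 0.2365 (plan: 0.236).
- De-escalation boundary: log[(1−φ)/(1−φ2)] / log[φ2(1−φ)/(φ(1−φ2))] = log(0.70/0.58) / log(0.294/0.174) = 0.3585 (plan: 0.359).

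The plan's figures reproduce. For a cohort of 3:

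- 1/3 = 0.333 lies between the boundaries, so stay. Recorded as 0/3, it becomes escalate.
- 2/3 = 0.667 is above the upper boundary, so de-escalate. Recorded as 1/3, it becomes stay.

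**Step 4. What does it do in BOP2?** In both arms the first look, at 6 patients, calls for a stop at 2 or more toxicities. A true 2/6 recorded as 1/6 no longer meets it.

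To show sensitivity only, I computed the chance of claiming the treatment acceptable exactly, from the printed boundaries at 6, 12, 18, 24 and 30 patients, for scenario 3 of each arm (toxicity 0.25). With full capture this gives 15.87% for AML (plan: 15.88%) and 12.50% for MDS (plan: 12.85%), so the method reproduces the plan closely. I then multiplied the toxicity probability, and its joint probability with response, by an **assumed** capture share. The documents give no such share.

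| Assumed DLT capture | AML (response 0.40) | MDS (response 0.30) |
|---|---|---|
| 100% | 15.9% | 12.5% |
| 95% | 19.2% | 15.3% |
| 90% | 23.1% | 18.5% |
| 80% | 31.9% | 26.1% |

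**The case against.** The strongest reply is that nothing is lost.

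- **Source records.** Section 7.5.1 requires source documentation and attribution for every adverse event, and 7.5.1.5 requires causality for each. This stands against the inference that the 6.2 analysis cannot be produced at all. The events exist and could be abstracted. What is missing is any provision for doing so.
- **Rarity.** The DLT in question must meet several conditions at once, and the same investigator judges both the drug relationship and the alternative cause. Electrolyte DLTs already require possible relatedness under 6.2.1, so they have no attribution gap. This stands: the gap is narrow.
- **Other routes.** No text says DLT counts come only from the item 3 list. Section 8.5 requires an efficacy/safety summary to the IND Office, whose approval is needed after every 3 evaluable patients before changing dose level. This stands in part, because the DLT content of that summary is not stated.
- **Non-binding boundaries.** The BOP2 go/no-go criteria are described as non-binding. This stands: a missed event removes a signal and does not by itself dictate continuation.
- **Section 8.5** does not itself promise a table of all events. True, but 6.2 does, and 8.5 adds no restriction that would reconcile the two.

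A reader might also infer that DLTs will be lost regularly, or that the printed operating characteristics are wrong. The documents support neither. The characteristics reproduce, and the capture shares above are assumptions.

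**Conclusion.** The point holds in two parts of unequal weight.

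The main part is textual and needs no assumption. The set of events in 6.2 is wider than the set that 7.5.1 items 3 and 4 put in the CRF, so CRF tables titled as all adverse events would understate incidence. The size of the shortfall cannot be estimated from the documents. The hematologic exclusion is probably the larger contributor in these populations.

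The second part, an uncollected DLT, is real on the wording but should be rare. It matters because single events change decisions: 1/3 to 0/3 in BOIN, and 2/6 to 1/6 at the first BOP2 look. It rests on the assumption that DLT counts are drawn from the CRF, which the plan neither states nor rules out. The plan should be corrected. The issue does not undermine the design.

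**What to change.** Both parts are needed, because each repairs only one half.

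1. Restate 6.2 as the incidence and severity of adverse events collected under 7.5.1. Name the item 3 filter and the item 4 hematologic exclusion there, and label the safety tables under 8.5 to match.
2. Add to 7.5.1 item 3 any grade 3 or higher non-hematologic event or laboratory value in the DLT monitoring window, regardless of attribution. The window is cycle 1 in phase 1b and the first 3 cycles in phase 2. Add a DLT yes/no field tied to 6.2.1.

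The first part is wording only. The second costs modest extra data entry. Neither changes treatment, the DLT definition or the stopping boundaries.
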